## Analysis Plan

To assess Aim 1, we will test the main and interactive effects of counseling intensity, NRT intensity, SmokefreeTXT, and engagement incentives on biochemically confirmed, 7-day point-prevalence abstinence at 6-month follow-up. Secondary abstinence outcomes are self-reported point-prevalence abstinence 12-weeks post-quit and continuous abstinence between months 1 and 6 post-quit.

*Measures, Populations and Analysis:*

Data for the primary, abstinence-focused analyses will include randomized levels of the treatment factors and their interactions as independent variables, binary abstinence outcomes based on self-reported abstinence (at 12-week follow-up) and biochemical verified abstinence (at 26-week follow-up only) as the dependent variables, and covariates such as demographics and smoking history collected at registration or enrollment.

The population will be the eligible, consented, enrolled subjects who were randomized to treatment. Participants who were randomized but did not complete the study will be included in analyses (unless they requested that their data not be used upon withdrawal from the study). Analyses will occur in the full intent-to-treat sample.

Logistic regression analyses will be used to estimate intervention main and interactive effects on binary abstinence outcomes. Both unadjusted models and models adjusted for covariates will be run. Separate models will be run for different outcomes (e.g., biochemically confirmed abstinence at 26-weeks post-quit, self-reported abstinence at 12 weeks post-quit, continuous abstinence between 4 and 26-weeks post-quit) under different assumptions regarding missing abstinence data (e.g., assuming all missing are smoking, assuming 80% of missing are smoking, using multiple imputation).

*Data Sources and Collection:* The primary outcome data will be collected by UW-CTRI via telephone follow-up interview and in-person, mailed, or emailed validation of abstinence via CO breath testing and/or urinary or salivary cotinine testing. Covariates will be assessed by WTQL staffers at registration or enrollment and transferred securely to UW-CTRI for analysis.

To assess Aim 2, we will evaluate the costs and cost-effectiveness of each intervention component overall and in the context of the other components (i.e., additive and interactive effects and their impact on cost-effectiveness).

*Measures, Populations and Analysis:*

Cost data will come from: research participants who will report on their out-of-pocket costs of tobacco and treatment and health care utilization at enrollment and follow-up; Optum who will report on intervention delivery, supply, and support costs; SmokefreeTXT who will report minute/data use costs associated with cumulative message volume and the estimated cost per user for the program; and from public data sources (on the costs and savings associated with cessation and continued smoking).

The population will be the eligible, consented, enrolled subjects who were randomized to treatment. Participants who were randomized but did not complete the study will be included. Analyses will occur in the full intent-to-treat sample whenever possible, using model estimation that permits missing data. Utilization rates have important implications for intervention costs, so both low and high utilizers of intervention components will contribute important data to these analyses.

Cost and efficacy data (abstinence outcomes assessed in Aim 1) will be used to estimate the costs per verified quit by treatment condition, in accordance with recommendations for cost-effectiveness analyses. These data will also be used to estimate costs per quality-adjusted-life-year (QALY) saved, based on prior estimates of QALY associated with smoking status. As recommended by Feirman et al. sensitivity analyses will be conducted, using alternative QALY measures to assess robustness of estimates. We can

use data from the project's factorial design to generate smoothed estimates of the costs per quit and costs per QALY for different combinations, using multivariate regression analysis. We will also estimate potential savings related to reduced smoking levels, as a function of previous smoking frequency and the estimated effects of the interventions on quitting or self-reported post-intervention smoking frequency. This approach could use information from the factorial design to create smoothed estimates of personal savings.

***Data Sources and Collection:*** Participants will self-report health care utilization and spending on tobacco and cessation treatments; Optum will report on WTQL intervention costs; and SmokefreeTXT will report on the volume of text message exchanges and total costs per user. UW-CTRI will collate data from these sources for analyses.

To assess Aim 3, we will identify demographic and smoking history moderators of treatment engagement and response and mediators of intervention effects (e.g., treatment engagement) on 6-month abstinence. Such analyses examining treatment by moderator interactions or examining treatment effects in subgroups of participants (e.g., the uninsured versus Medicaid-eligible; men versus women) will identify sub-populations that may not benefit equally from enhanced WTQL services using data collected by the WTQL at registration or study enrollment. We will also explore the extent to which treatment engagement (measured throughout counseling and SmokefreeTXT and at follow-up for medication) and cessation motivation and confidence (assessed at follow-up) differed across treatment conditions, and the extent to which such differences may mediate or account for treatment effects on abstinence.

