### **II. GOALS/AIMS**

The overarching aim of the proposal is to evaluate ways to enhance quit line treatment for low-income smokers in terms of abstinence, costs, and reach. The specific aims of the project are listed below.

1. To assess the main and interactive effects of the four experimental factors (see below) on biochemically confirmed, 7-day point-prevalence abstinence at 6-month follow-up among low-education, uninsured, or Medicaid-eligible smokers who relapse following a standard WTQL intervention. Secondary abstinence outcomes are self-reported point-prevalence abstinence 12-weeks post-quit and continuous abstinence between months 1 and 6 post-quit.

Factors	Levels
1. Quit line counseling intensity	1. 1 vs. 4 proactive counseling calls
2. Nicotine replacement therapy (NRT) intensity	2. Patch (2 wks) vs. Patch+ Lozenge (4 wks)
3. SmokefreeTXT text messages	3. Proactive enrollment vs. none
4. Financial incentives for treatment engagement	4. \$30-\$150 vs. none
2. To evaluate the cost-effectiveness of each intervention component overall and in the context of the other components (i.e., additive and interactive effects and their impact on cost-effectiveness). The aim is to develop data to inform future quit line care planning and policy.	
3. To identify demographic and smoking history moderators of treatment engagement and response and mediators of intervention effects (e.g., treatment engagement) on 6-month abstinence. This aim will identify sub-populations that may not benefit equally from enhanced WTQL services and will suggest ways to refine the treatments to enhance their efficacy.	

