## Treatment procedures description

The WTQL offers a standard, evidence-based protocol comprising a single 20-minute counseling call (plus *ad hoc* calls as initiated by the participant) and a two-week supply of an over-the-counter nicotine replacement therapy. This will be the treatment that all study enrollees will receive in the 2.5-18 months preceding study enrollment and will be the base treatment in the second round of intervention to be evaluated in terms of reach, efficacy, and cost-effectiveness in the proposed study. Four interventions will be evaluated in a fully crossed design:

- Augmented counseling (4 proactive, scheduled telephone counseling sessions with a quit coach rather than the usual-care 1 call). The content of this counseling will follow existing, evidence-based protocols used by the WTQL in states that contract for this more intensive service.
- Augmented nicotine replacement therapy (4 weeks of nicotine patch plus nicotine mini-lozenge rather than the usual-care two-week supply of nicotine patch therapy), for those meeting WTQL NRT eligibility criteria. These FDA-approved, over-the-counter medications will be dispensed with instructions to use that follow package insert specifications (e.g., using lower, 2-mg dose mini-lozenges for individuals who do not smoke within 30 minutes of waking; dispensing lower, 14-mg dose patches to individuals who smoke fewer than 10 cigarettes per day), in accordance with current WTQL practice and documentation.
- Adjunctive SmokefreeTXT support (proactive enrollment in this 6-8-week text message-based cessation support program versus none). This national program is offered at no cost to users (apart from data/minute costs charged by cellular providers about which enrollees are advised at enrollment) and is sponsored by the National Cancer Institute. This program sends up to 5 messages per day for up to 2 weeks prior to the target quit day and 6 weeks following the target quit day (total duration may be longer if participants elect to change the target quit day). The text messages offer tips to help enrollees achieve their goal of quitting smoking and offer real-time interactive tips when participants text in responses indicating cravings, negative moods, or slips. Participants have the option to reset quit dates and have the option to unsubscribe at any time by texting STOP to the program.

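### Aim 2 asks what each component adds for its cost, but the only per-quit ratio the plan commits to is a level by condition, with no incremental ratio, stated reference or sampling-uncertainty method

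*Combined protocol and SAP*

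**What the plan says.** Section II (Goals/Aims) sets Aim 2 as "To evaluate the cost-effectiveness of each intervention component overall and in the context of the other components", and adds that this covers additive effects, interactions and what both do to cost-effectiveness. Its purpose is practical: "The aim is to develop data to inform future quit line care planning and policy". The Analysis Plan repeats the commitment: "we will evaluate the costs and cost-effectiveness of each intervention component overall and in the context of the other components", with the same reference to additive and interactive effects.

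Under Aim 2, the Analysis Plan then describes the outputs:

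- Cost and abstinence data "will be used to estimate the costs per verified quit by treatment condition, in accordance with recommendations for cost-effectiveness analyses". This is the only per-quit ratio stated as something that will be done.
- Cost per QALY saved will be estimated, with no comparator named.
- For robustness, "sensitivity analyses will be conducted, using alternative QALY measures to assess robustness of estimates".
- The factorial data can be used for "smoothed estimates of the costs per quit and costs per QALY for different combinations". The text presents this as possible, not as planned.
- Savings from reduced smoking will be estimated, drawing on the estimated effects of the interventions.

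The Treatment procedures description says of standard quit line care that it "will be the base treatment in the second round of intervention to be evaluated in terms of reach, efficacy, and cost-effectiveness". The Aim 2 text does not name it as the reference. No section gives an incremental cost per additional quit, or an interval or other method for sampling uncertainty in costs or ratios.

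**The concern.** The aim is about contributions: what a component buys when added, alone or alongside others. The committed ratio divides a condition's whole cost by all its quits. Every enrollee receives at least standard care (section D, Randomization), so both parts of that ratio include what the base treatment costs and achieves. A quit line deciding whether to pay for extra calls, lozenges, texts or incentives needs added cost over added quits. The level answers a different question.

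Uncertainty is the second gap. Varying the QALY measure addresses one input to one of the ratios. It says nothing about sampling error in the quit difference, which is the denominator of any incremental ratio and may lie close to zero. It also says nothing about sampling error in cost, although the plan itself notes that "Utilization rates have important implications for intervention costs".

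**Working it through.** The plan gives no cost-effectiveness figure, quit rate or cost per component, so there is no figure of its own to reproduce. The dollar results below are illustrations.

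**Inputs from the document.** The target sample is 1,408 to 1,600 (section A). With equal allocation assumed, each factor level has 1,408/2 = 704 to 1,600/2 = 800 participants. The incentive maxima in the section F table are $60, $30, $60, $30, $150, $120, $150 and $120, with mean 720/8 = $90.

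**Assumed inputs.** Base cost C0 is $50, $100 or $200. Base quit rate E0 is 5%, 10% or 15%. Gain dE is 2, 4 or 6 percentage points. Added cost dC is $30, $60, $90, $120 or $150, which are the incentive maxima and their mean at full payout. The document gives no costs for calls, medication or texts.

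**Step 1: when the two ratios differ.** The level is (C0 + dC)/(E0 + dE) and the incremental ratio is dC/dE. For dE > 0, dC/dE > (C0 + dC)/(E0 + dE) is the same as dC·E0 > dE·C0, that is, dC/C0 > dE/E0. This rule needs no assumed values. At C0 = $100 and E0 = 10%:

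- dC = $150, dE = 2 points: level 250/0.12 = $2,083; incremental 150/0.02 = $7,500, or 3.6 times the level.
- dC = $30, dE = 6 points: level 130/0.16 = $813; incremental 30/0.06 = $500, or 0.62 times the level.

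**Step 2: ranking.** At the same base values, take component A (+$60, +2 points) and component B (+$120, +6 points).

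- A: level 160/0.12 = $1,333; incremental 60/0.02 = $3,000.
- B: level 220/0.16 = $1,375; incremental 120/0.06 = $2,000.

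The level favours A and the incremental ratio favours B. To see how typical this is, combine the five added costs with the three gains. This gives 15 options and 15 × 14/2 = 105 pairs, in each of nine base settings, or 945 pairs. The order reverses in 48 (5.1%): 5 of 105 at $100 and 10%, and at most 11 of 105 in any setting.

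**Step 3: sampling uncertainty for one factor, on versus off.** SE = √[p0(1 − p0)/n + p1(1 − p1)/n], with 95% limits dE ± 1.96·SE. For 10% versus 12% and n = 800, SE = √[(0.0900 + 0.1056)/800] = 0.0156, giving limits of −1.1 to 5.1 points. The lower limits for a 2-point gain, in points, are:

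| Base quit rate | n = 704 | n = 800 |
|---|---|---|
| 5% | −0.5 | −0.3 |
| 10% | −1.3 | −1.1 |
| 15% | −1.8 | −1.6 |

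All six lie below zero, so the incremental ratio has no finite upper limit. The chance of an observed difference of zero or less is 5% to 16% across these cases.

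For a 4-point gain the limits are finite but wide. At a 10% base rate they are 0.6 to 7.4 points (n = 704) and 0.8 to 7.2 points (n = 800). With added cost fixed at $90 and unrounded limits, this is about $1,220 to $14,700 and $1,250 to $11,000 per additional quit. Sampling error in cost is left out.

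**The case against.** The strongest reply is that the plan already intends component contrasts. Its Aim 2 statement refers to additive and interactive effects, which in a factorial design are on-versus-off contrasts. The savings estimate is firm and rests on intervention effects, and QALYs saved is comparative wording. Each factor has an evident lower level, and cell 4 (one call, two-week patch, no texts, no incentives) is an evident reference. The plan also defers to published recommendations, which may call for incremental ratios and uncertainty analysis. Costs and quits for all 16 cells would in any case yield every incremental ratio by subtraction and division.

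Much of this stands. A reader might infer that the plan has no comparator in mind, or that its data cannot answer Aim 2. The documents do not support either reading. But the intention does not reach the description of outputs: the only committed per-quit ratio is by condition, and the regression-based alternative is optional and still given per combination. The content of the cited recommendations cannot be checked here. The provisions for missing data, and the alternative QALY measures, do not address sampling error in a cost ratio.

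The illustrations also have limits. The ranking pair was chosen to show a reversal, and reversals are uncommon on the grid. Added costs reflect incentives only.

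**Conclusion.** The point holds as a mismatch between the aim and the stated estimate. Followed literally, cost per verified quit by condition does not show what a component adds for its cost, and no method is given for the sampling uncertainty of any ratio. The direction rule is exact. The dollar amounts, the 5% reversal frequency and the intervals rest on assumed costs, quit rates and gains, with equal allocation.

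Two stronger readings are tempting and should be resisted. One is that the level always makes a component look cheaper than it is; the rule shows that the gap runs either way. The other is that decisions based on the level would usually be wrong; on the grid, most pairs keep their order. The matter should be corrected because Aim 2 is a specific aim with its own planned article and a policy purpose. The abstinence analysis under Aim 1 is not affected.

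**What to change.** Revise the Aim 2 part of the Analysis Plan as follows:

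- Make the main estimate the incremental cost per additional verified quit, and per QALY, for each factor on versus off, averaged over the other factors in the factorial model.
- Report incentives also by counseling and texting level, because the maximum payout runs from $30 to $150 by design.
- For combinations, give model-based estimates against a stated reference, such as base treatment only (cell 4).
- Report joint uncertainty in the cost and effect differences in a form that still works when the quit difference is near zero, for example a bootstrap of the pair or net benefit over a range of values per quit.
- Keep cost per quit by condition as description.
- If the cited recommendations already require these steps, say so in the plan.

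The cost is analysis-plan wording and modest extra programming on data already planned. The drawback is that intervals will be wide and, for a small effect, may have no finite upper limit.

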***Measures, Populations and Analysis:***

Self-report demographic, smoking history, health status, psychiatric history, and texting use collected at WTQL registration or study enrollment will be examined as candidate moderators of treatment response. Mediators (treatment engagement; perceived support; reduction in exposure to smoking/triggers; quitting motivation and confidence) will be assessed during treatment (in the case of treatment engagement) or during follow-up telephone interviews at 12- and 26-weeks post-quit.

The population will be the eligible, consented, enrolled subjects who were randomized to treatment. Participants who were randomized but did not complete the study will be included (unless they requested that their data not be used upon withdrawal from the study). Analyses will occur in the full intent-to-treat sample whenever possible, using model estimation that permits missing data.

Evaluation of moderators will be accomplished with moderated logistic regression models that include effect-coded intervention main and interaction effects on abstinence, a given moderator, and interactions of the moderator with the intervention effects. Mediation analyses will include linear regression models in which mediators are regressed on intervention main effects and interactions, logistic regression models in which binary abstinence outcomes are regressed on both intervention variables and mediators, and estimates of the mediated effect. Formal mediation analysis computed via the SAS PROCESS macro.

***Data Sources and Collection:*** Candidate moderators will be assessed via participant self-report by the WTQL during initial registration or study enrollment. Treatment engagement mediators will be assessed by the WTQL (for counseling completion), SmokefreeTXT (for SmokefreeTXT completion and interactions), and by UW-CTRI at follow-up telephone interviews (for self-reported patch and mini-lozenge use). Other candidate mediators

(cessation motivation and confidence) will be assessed by UW-CTRI during 12- and 26-week telephone follow-up interviews.

*Products in the Evaluation/Research Reports:* We anticipate writing at least four different research articles for publication in peer-reviewed journals based on this project. Aim 1 results regarding intervention efficacy will be published in a single manuscript. Aim 2 results regarding costs and cost-effectiveness will be published in a separate manuscript. Aim 3 results on moderators of intervention effects will be published in a third manuscript and mediation results will be published in a fourth manuscript. It is also possible that we will publish a separate protocol and process description of the experimental study while the study is underway.

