### **Assessment Plan**

1. Baseline assessment (See uploaded registration data from the WTQL). Specific fields collected at initial registration for WTQL services will be pulled for study use and analyses. These items include age; gender; race; ethnicity; county; education; insurance status (uninsured, in BadgerCare Plus/Medicaid, or privately insured (if low in education)); chronic health conditions; registration date; how heard about WTQL; and smoking history (multiple items). These data will be collected for all consented enrollees and patient-level data without direct identifiers will be collected for those who are unreachable, are ineligible, or decline to enroll.
2. Enrollment assessment (see uploaded Post Consent Baseline assessment). Following oral consent, additional data that are not routinely assessed at the standard post-WTQL enrollment follow-up will serve as baseline assessments for the evaluation study. Items include a detailed assessment of smoking in the past 7 days (how many cigarettes smoked on each day) and other current eligibility criteria. In addition, items will assess supplemental indicators of socioeconomic status, recent use of nicotine products and smoking cessation therapies and associated costs, use of healthcare over the past 6 months (for cost-effectiveness analyses), frequency of texting, indicators of relapse proneness, brief psychiatric

status/history screener (without questions on illicit substance use), and menthol cigarette use. The WTQL will also confirm registration data whenever someone re-enrolls in treatment, as per their standard protocol. The target quit date will also be collected.

3. Engagement assessment. Engagement will be tracked using data routinely collected in the course of existing services, including the number and duration of WTQL calls completed and use of the WTQL Text2Quit program (among 18-24 year olds who enroll in this program outside of their study enrollment call, which is possible), the duration of enrollment in SmokefreeTXT and the number and content (e.g., craving or mood ratings; smoking status reports; requests for help with craving, mood, or slips) of inbound, subject-generated messages to SmokefreeTXT. Medication use will be assessed via self-report at 12- and 26-week follow-up telephone interviews.

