4. Follow-up assessment (see uploaded follow-up assessment). At 12- and 26-weeks following the target quit day, participants will be asked to report on recent use of tobacco and smoking cessation products and associated costs, treatment satisfaction, and levels of candidate mediators of intervention effects (nicotine withdrawal distress, confidence, motivation, exposure to smoking triggers, and perceptions of stress, support, or control). Participants will earn \$30 for completing each of these calls. At the 12-week call, participants will also be asked whether the research team may email them reminders about the final follow-up at 26 weeks.

At 26 weeks following the target quit day, individuals claim to have not had even a puff of a cigarette in the past 7 days may be asked to schedule a verification visit at which they will be asked to provide a breath sample for carbon monoxide (CO) testing using the commercially available Micro+Smokerlyzer® from Bedfont Scientific Ltd. and a urine sample for cotinine testing to confirm abstinence. These biochemical verification procedures present minimal risk, as they require only that participants hold their breath for 15 seconds before blowing into a CO detector and that participants urinate in a cup. In order to achieve a high level of abstinence verification, and in light of participant travel involved, participants will receive \$40 for completing this visit. Participants may be asked to complete alternative testing to verify abstinence remotely. This may entail mailing back a saliva sample for cotinine testing or emailing the research team a CO test using a personal CO monitor, and will similarly earn participants \$40.

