Collect Baseline Data (Attach- ment F)	
 
• Socioeconomic indicators (income, employment)
 
• Cessation history
 
• Recent nicotine & e-cig product use and costs
 
• Past 6-mo healthcare use
 
• Frequency of text messaging
 
• Psychiatric history
 
• Perceived stress
 
• Menthol use
 
• Indicators of relapse proneness (e.g., exposure to others smoking, craving when abstinent)
 
• Use and costs of stop-smoking treatments since last QL call
 
• 1-3 collateral names & phone numbers
 
	WTQL
Initiate Treatment	
 
• Randomize to treatment
 
• Schedule first/only WTQL counseling call
 
• Describe medication regimen
 
• Describe assessment schedule
 
• Describe incentives schedule, if applicable
 
• Ask patients if want information about how to enroll in SmokefreeTXT, if applicable
 
	WTQL
Welcome Mailing (Attach- ments B- D)	
 
• Medication (sent in a separate package to those medically eligible)
 
• Medication instructions, if applicable
 
• Target quit date & follow-up reminders
 
• Contact information for WTQL & UW-CTRI (to reduce call rejection)
 
• Incentive reminders, if applicable
 
• SmokefreeTXT description, terms of use & privacy policy, if applicable
 
• Study information sheet containing all required elements of consent and HIPAA authorization
 
	WTQL
12-Week Follow Up (Attach- ment G)	
 
• Self-reported tobacco use & costs in past 7 days & since target quit date
 
• Treatment use, adherence, satisfaction, & costs
 
• Candidate mediators (perceived Quit Coach support; reduction in exposure to smoking/triggers; quitting motivation & confidence)
 
	UW- CTRI

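### No baseline measure of quitting motivation or confidence is listed or adjusted for in the Aim 3 mediation models, so mediation through them can be created or inflated for any factor that shifts them

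*Combined protocol and SAP*

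**What the plan says.** The measures paragraph for Aim 3 (Analysis Plan) reads "Mediators (treatment engagement; perceived support; reduction in exposure to smoking/triggers; quitting motivation and confidence) will be assessed during treatment". The sentence goes on to tie that timing to treatment engagement alone and gives the other mediators the timing "or during follow-up telephone interviews at 12- and 26-weeks post-quit".

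The other statements of timing agree:

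- The Aim 3 introduction speaks of whether "cessation motivation and confidence (assessed at follow-up) differed across treatment conditions".
- The Aim 3 data-sources paragraph states "cessation motivation and confidence) will be assessed by UW-CTRI during 12- and 26-week telephone follow-up interviews".
- Assessment Plan item 4 (follow-up) lists "levels of candidate mediators of intervention effects (nicotine withdrawal distress, confidence, motivation, exposure to smoking triggers".
- The 12-week and 26-week rows of the Schedule of Study Activities both list motivation and confidence.

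The baseline is described twice:

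- Assessment Plan item 2, "Enrollment assessment (see uploaded Post Consent Baseline assessment", covers socioeconomic items, product and treatment use, health care use, "frequency of texting, indicators of relapse proneness, brief psychiatric" items and menthol use.
- The baseline row of the Schedule adds perceived stress and "Indicators of relapse proneness (e.g., exposure to others smoking, craving when abstinent".

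Neither list names motivation or confidence. Both are worded as open lists, and the form itself is an upload that is not part of the documents.

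The Aim 3 models are a linear regression of each mediator on the randomized factors and their interactions, and a logistic regression of abstinence on factors and mediators. No baseline covariate is named for either. The covariates that the plan gives as examples, under Aim 1, are demographics and smoking history.

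**The concern.** A mediated effect is the product of two slopes: treatment to mediator, and mediator to abstinence. Randomization to the 16 cells (section D) makes the first slope unbiased. It does nothing for the second, because nobody is randomized to a level of confidence. People who were confident before treatment will tend to be confident at week 12 and also more likely to quit. With no baseline value in the model, the second slope absorbs that difference, and any factor that raises confidence will seem to work partly through it, even if confidence has no effect on quitting.

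The Goals/Aims section says Aim 3 should suggest how to refine the treatments, and mediation is to have its own paper. An inflated mediated effect could direct that refinement to the wrong target. A pre-randomization value that was not collected cannot be recovered later.

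**Working it through.** The documents give no effect size, power or other figure for mediation, so there is no stated figure to reproduce. The check is of direction and plausible size, by simulation.

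**Inputs.** From the documents: N = 1,408 (lower end of the target in section A), randomized factor levels, and the two regressions named for Aim 3. Everything else is assumed. One two-level factor T, coded −0.5/+0.5, is used, with complete follow-up.

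**Model.** C is baseline confidence (SD 1) and M is confidence at follow-up (SD about 1).

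- Mediator: M = a·T + g·C + error
- Outcome: logit P(abstinent) = −2 + 0.2·T + b·M + h·C
- Mediated effect = a × b

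The intercept gives 1/(1 + e²) = 12% abstinent at average values. Both regressions were fitted without and with C, 1,000 trials per setting. Mediation was declared when both slopes were significant at two-sided 0.05.

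**1. Treatment does not move the mediator (a = 0).** Without C, the mean mediated effect is about zero (−0.0003 to 0.0018), and mediation is declared in 1% to 5% of trials. This holds although the mediator-to-abstinence slope is biased: a true 0 is estimated as 0.09 to 0.34.

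**2. Treatment moves the mediator (a = 0.2), but the mediator has no effect (b = 0, true product 0).**

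| g, h | slope b without C | product without C | declared without C | declared with C |
|---|---|---|---|---|
| 0.3, 0.3 | 0.085 | 0.017 | 17% | 5% |
| 0.5, 0.5 | 0.245 | 0.049 | 83% | 5% |
| 0.7, 0.5 | 0.347 | 0.070 | 96% | 4% |

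The product follows from the slopes. In the second row, for example, 0.198 × 0.245 = 0.049.

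**3. Mediation is real (a = 0.2, b = 0.3, true product 0.2 × 0.3 = 0.06).** Without C the product is estimated as 0.077, 0.107 and 0.127. That is 0.077/0.06 = 1.3, 0.107/0.06 = 1.8 and 0.127/0.06 = 2.1 times the truth. With C it is 0.059 to 0.060.

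**4. Dependence on the assumed shift.** A second set of runs took weaker confounding: baseline to week-12 correlation 0.3 to 0.5, log-odds 0.2 to 0.4 per SD of baseline confidence, true mediation zero, a Monte Carlo interval for the product, and 400 trials per setting. Without C, mediation is falsely significant as follows:

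- shift of 0.25 SD: about 10% to 70% of trials (about 5% with C)
- shift of 0.10 SD: 3% to 29%
- no shift: 0% to 2%

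**5. What baseline adjustment does not repair.**

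- If the baseline item has reliability 0.6 (assumed), the adjusted false-positive rate at the strong end of item 4 with a 0.25 SD shift is about 20%, not 5%.
- The 12-week interview records confidence alongside smoking since the quit date, so being quit may raise confidence. If it does so by 0.5 SD (assumed), with no true mediation, false mediation is significant in 97% to 99% of trials even with a perfectly measured baseline.

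**The case against.** The strongest reply is that randomization balances baseline confidence. A reader might infer that pre-existing confidence would be credited to the treatments as such. That does not follow: where a factor leaves confidence unchanged, the false mediated effect is about zero (items 1 and 4). The bias needs a factor that truly shifts the mediator.

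A reader might also infer that no baseline measure exists. The documents support only that none is listed. The baseline form is an unseen upload, its lists are open, and registration smoking history is described only as several items. Even so, the plan assigns these two measures to UW-CTRI, whose participant contact is follow-up interviews and verification. If baseline items do exist, the regressions still do not name them.

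The rates rest on chosen inputs, and a small shift with weak confounding gives no excess over 5%. That stands, so the figures illustrate sensitivity and do not estimate what will happen in this trial.

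Baseline adjustment is also not a full cure. Item 5 shows why, and adjusted results should not be presented as causal.

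The exposure mediator is a weaker case. Baseline exposure to others smoking is listed, and no document defines the reduction as a subtraction. What remains is to confirm that the items match.

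Finally, the plan describes mediation by motivation and confidence as something to explore, and its example mediator under Goals/Aims is engagement. This limits the stakes but does not remove the bias.

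**Conclusion.** The point holds in a conditional form. As written, motivation and confidence are scheduled only after treatment, no baseline counterpart is listed, and the mediation regressions name no baseline adjustment. The mediator-to-abstinence path is therefore open to confounding by pre-existing motivation and confidence. For any factor that shifts these mediators, apparent mediation can be created or overstated.

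The upward direction requires only that baseline confidence predict later confidence and abstinence with the same sign. The size cannot be fixed from the documents. In the settings tried where treatment shifts the mediator, false-positive rates run from 3% to 96%, and real mediation is overstated by a factor of about 1.3 to 2.1 in item 3. The Aim 1 comparisons of randomized factors are untouched. This should be corrected, but it does not threaten the primary result.

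**What to change.** 1. Confirm that the motivation and confidence items used at week 12, and matching exposure items, are on the post-consent baseline form. If they are not, add them before randomization.
2. Include each mediator's baseline value as a covariate in both the mediator regression and the abstinence regression.
3. Make the 12-week mediator with 26-week abstinence the main mediation analysis. The 26-week mediators come from the same interview as the abstinence report, so their order is unclear.
4. Report all mediation by motivation and confidence as exploratory and associational, for every participant and not only for those without baseline items.
5. Add a sensitivity analysis for residual mediator-outcome confounding and one for reverse causation, for example accounting for smoking status at week 12. That status may itself lie on the causal path, so the second analysis probes the result and does not settle it.

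The cost is about a minute more on a call that is already made, one covariate per mediation model, and slightly more analysis work.
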